We recognise that not all people who have a cervix or vagina identify as women.

Methods

This is a prospective study observing the impact of the change from cervical screening utilising cervical cytology with a speculum examination to the implementation of hrHPV testing including the option of vaginal self-testing, in the primary care setting. This will include at least 15 general practice clinics in 3 regions of NZ and aims to screen at least 3000 people. The study team wish to take a pragmatic

approach and intend to work collaboratively with local providers and their Māori advisors to assist the introduction of the changes. We will collect real world data that will inform the wider implementation of hrHPV screening to the NCSP. This will be done without additional resource other than support for study consent and data collection. Operational procedures and clinical management of the patients will be determined by the providers involved within guidelines agreed between the study team and the NCSP on a business as usual basis. Prospective data collection will be performed by providers and supported by the study team. As this is not a comparative study, data analysis will be largely descriptive. The data will be presented in the context of historical coverage data available from the NCSP.

As the NCSP Register (NCSPR) is not currently able to manage the results of hrHPV screening, this information will be overseen by the study team. The study team will act in place of the NCSPR to provide reminders to the practices when patients are overdue further investigations or repeat testing, and to ensure management recommendations are correct. Following colposcopy or on completion of the study when the NCSPR is able to manage these patients, information they will be referred back to the NCSPR. This surveillance and tracking will be in addition to the normal recall processes used by individual practices.

Practice selection

Consent to participate in the Study will be sought from approximately 15 practices with an aim to recruit approximately 3000 patients over 6 months. The 15 practices will be selected from 3 regions with 5 practices each being selected from the Whanganui, Capital & Coast, and Canterbury District Health Board (DHB) regions. For patients eligible for cervical screening, the selected practices will offer a choice of hrHPV-self-testing within the practice or at home or a clinician-taken cervical hrHPV test.

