The study aims to include patients from a cross-section of demographic characteristics. To ensure representation from practices with a higher proportion of Māori and Pacific patients, from rural locations, and with higher levels of social deprivation, the demographic characteristics of each practice was investigated and categorised by the following variables:

- Rural location
- Urban location + higher proportion of women with a mixed/high socioeconomic index
- Urban location + higher proportion of women with a low socioeconomic index
- Proportion of Māori women enrolled at or higher than the overall proportion of Māori in the NZ population (16.5%)
- Proportion of Pacific women enrolled at or higher than the overall proportion of Pacific in the NZ population (8.1%)

In Whanganui, following discussion with iwi representatives, five practices were selected by the Whanganui Leadership Team which represent the 6 iwi in the region. Screening for cervical cancer using hrHPV testing is seen as significant opportunity to address existing and emerging inequality. This screening approach has the capacity to improve participation for Māori and other under-screened populations. The hrHPV pilot provides an opportunity for Māori patients and other under-screened patients to be included in community engagement with the research study. The development of a

locality leadership approach in Whanganui provides the opportunity for an integrated iwi, community and GP clinic approach for screening to develop. The Whanganui hrHPV study steering group has included GP clinics in the study that will reflect this approach and demonstrate an emerging integrated model of care.

The Whanganui population has a high representation of Māori women and rural practice. In order to provide a balance in demographics, as reported in the aims, in Capital & Coast and Canterbury, four practices from each region would be selected at random, but an additional practice in each region would be chosen at random from within practices with a higher than population level of eligible Pacific women enrolled. In all cases, if a selected practice does not consent, then another practice with a similar demographic profile will be randomly selected.

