It is acknowledged that providers may be small or large, and that the number of practices may need to be revised to ensure that the screen sample is of adequate size. Resources will vary between practices and financial support to practices will be proportional to the number of patients recruited.

Practices must hold a screening register/ recall system from which eligible patients can be identified and historical comparison can be made (5 years preferable).

Practices and PHO staff must agree to take part according to study protocol.

Within each practice (or group of small practices) a site lead and a principal screener will be identified.

Support to Screen outreach services will also conduct the study on behalf of selected practices (including, consent, hrHPV testing, and hrHPV test result follow up) . In these circumstances a formal process for clinical responsibility between the outreach service, GP clinic, and the University of Otago study team will be agreed.

Patient selection

Inclusion Criteria

People enrolled in the practice who are eligible for cervical screening as part of the NCSP* and are recalled for cervical screening or opportunistically attend the provider and are due for a cervical screen within the study enrolment period.

Participants are eligible to take part from four months prior to when their cervical screen is due, as per NCSP eligibility.

Participants must provide full informed consent.

Notes

Patients who are recalled for screening but report symptoms at the time of their screening test will be eligible for the study, however a strong recommendation for a clinical assessment will be made.

Patients who are invited to participate in this study can do so if they agree to participate within 3 months of the completion of the recruitment period (i.e., before 1 April 2023).

Patients attending for investigation of symptoms who are not due for screening are not eligible for the study. Note that cervical cytology may be taken as clinically indicated.

Patients who are unable or unwilling to provide informed consent will be recorded, but not included as study participants.

Common reasons a patient may be ineligible for NCSP cervical screening include:

- Total hysterectomy and no further cervical screening required
- Moved overseas
- Serious illness and further screening is not indicated
- Declined screening
- Referred to secondary care services / colposcopy
- Under specialist care

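### Practices were categorised to ensure that more deprived practices are represented, but no step of the practice selection secures this

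*Protocol*

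**What the plan says.** All of the selection rule is in the protocol, under Practice selection.

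- **Purpose.** The reason given for categorising practices is: "To ensure representation from practices with a higher proportion of Māori and Pacific patients, from rural locations, and with higher levels of social deprivation".
- **Categories.** Five are listed. They include "Rural location" and "Urban location + higher proportion of women with a low socioeconomic index"; the others are urban with mixed or high socioeconomic index, and Māori and Pacific shares at or above the national proportion.
- **Numbers.** "The 15 practices will be selected from 3 regions with 5 practices each being selected from the Whanganui, Capital & Coast, and Canterbury" regions.
- **Whanganui.** The regional leadership team chose five practices to represent the six iwi. The text credits the region with many Māori women and with rural practice. It does not mention deprivation.
- **The other two regions.** "four practices from each region would be selected at random, but an additional practice in each region would be chosen at random" among practices with above-population Pacific enrolment.
- **Refusals.** If a practice declines, "another practice with a similar demographic profile will be randomly selected".
- **Expansion.** The protocol accepts that "the number of practices may need to be revised" to reach an adequate sample, and gives no category rule for added practices.

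Under Outcome measures (Other), outcomes are to be presented by deprivation quintile, among other factors, where numbers permit.

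**The concern.** The stated purpose and the stated rule do not fit together. The purpose is to secure several kinds of practice, including more deprived ones. Of the categories drawn up for it, only Pacific enrolment enters a draw, and only for one practice in each of two regions. The categorisation by socioeconomic index was made and then not used to select anyone.

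The goal is to find where, and for whom, the screening pathway fails, and deprivation quintile is a planned reporting factor. The Impact of Covid 19 section also expects the results to guide where resources are needed. If the draw happened to include few or no low-socioeconomic urban practices, the study would have less information on screening in that setting, while the protocol would still tell its readers that representation had been ensured. Practice selection is fixed in the protocol itself, so this is not a detail that would be left to an analysis plan.

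**Working it through.** **The plan's own figures.** 3 regions × 5 practices = 15. Under Statistical Considerations, 1600 eligible patients on a three-year interval give 1600 / 3 = 533 due per year and 533 / 2 = about 266 in six months. With 25% not taking part, 266.7 × 0.75 = 200 per practice, and 15 × 200 = 3000. These figures reproduce. The protocol gives no figure for the number of more deprived practices.

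**How each of the 15 practices is chosen.**

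| Practices | Rule | Secures a more deprived practice? |
|---|---|---|
| 5, Whanganui | Purposive, by iwi representation | No rule stated |
| 8, the other two regions (4 each) | Unrestricted random draw | No |
| 2, the other two regions (1 each) | Random within above-population Pacific enrolment | No rule stated; some may be deprived |
| Replacements | Similar profile to the practice that declined | No; this keeps whatever profile was drawn |
| Added practices | None stated | No |

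**How often the random draws could miss the category.** Let p be the share of a region's practices in the urban low-socioeconomic category. The protocol does not give p, so 10%, 20% and 30% are assumptions, taken as equal in both regions.

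- None among four in one region: (1 − p)^4
- None among all eight: (1 − p)^8

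| Assumed p | None of 4 | None of 8 |
|---|---|---|
| 10% | 0.656 | 0.430 |
| 20% | 0.410 | 0.168 |
| 30% | 0.240 | 0.058 |

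**Finite-list check.** Drawing 4 without replacement from an assumed 20, 50 or 100 practices per region gives, for none of 8, 0.40 to 0.43 at p = 10%, 0.14 to 0.16 at 20% and 0.04 to 0.06 at 30%. The conclusion does not depend on the size of the list.

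**Limit of these figures.** They cover 8 of the 15 practices. The five in Whanganui and the two chosen for Pacific enrolment may also be deprived, so the chance that the whole study has no such practice is at most the eight-practice figure.

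**After the fix.** If each region has a willing practice in the category and one is required, the chance of none is zero by design.

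**The case against.** The strongest reply is that the rule is less loose than it looks. The categories are not ignored: Pacific share governs two draws, and profile governs every replacement. Whanganui's choice was deliberate and made with inequality in mind, so *left to chance* would be the wrong description there. Deprived patients can enrol at any practice, including rural ones and those with high Māori or Pacific enrolment. The study is descriptive, and no power figure changes. These points stand, and they limit the size of the concern. They do not supply a step that secures more deprived practices, which is what the text says was done.

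A reader might infer three stronger things that the protocol does not support.

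- *That rural practices outside Whanganui should have been secured.* The protocol aims for rural representation in the study, credits Whanganui (5 of 15 practices) with it, sets no per-region standard and lists no rural reporting stratum.
- *That the relevant risk is that at least one of the two regions misses the category.* That is a per-region standard the protocol never sets; the eight-practice figure is the closer one.
- *That the most deprived quintiles will be empty.* The quintiles describe participants and the category describes practices. Missing the category may thin those strata but does not empty them.

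Timing also counts. The version history entry for 2D is dated 1/3/23, and the notes to the Inclusion Criteria require invited patients to agree before 1 April 2023. The draw has therefore probably been made, and a redraw is unlikely to be available.

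**Conclusion.** The point holds for deprivation. The protocol claims to ensure representation of more deprived practices, and no stated step does so. With assumed category shares of 10%, 20% or 30% in each region, the eight unrestricted draws would contain no low-socioeconomic urban practice with probability 43%, 17% or 6%. These figures are illustrative: they rest on shares the protocol does not give, and they are an upper guide for the study as a whole. At the higher share the risk is small; at the lower shares it cannot be squared with the word *ensure*. The consequence is for the stated cross-section of practices and for how much the reporting by deprivation quintile can say. The sample size and the rest of the design are unaffected.

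**What to change.** 1. **Any draw still to be made.** In Capital & Coast and in Canterbury, require at least one of the four practices to come from the urban low-socioeconomic category already assigned, where the region has such a practice, and draw the rest at random. Keep the fifth, Pacific-enrolment draw. State it if a region has no eligible practice in the category.
2. **Added practices.** Apply the same rule if the number of practices is increased.
3. **Practices already drawn.** Report the number achieved per category and region, and replace the claim to ensure representation with what the draw delivered.

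**Cost.** Protocol wording, and a restricted instead of a simple draw from a list already categorised; no extra practices are needed. The downside is unequal selection probabilities, which should be recorded. For example, with an assumed 50 practices in a region, 10 of them in the category, suppose one is drawn from the category and three from the remaining 49. A category practice then has probability 1/10 + (9/10) × 3/49 = 0.155 and any other 3/49 = 0.061, before the Pacific draw. Check: 10 × 0.155 + 40 × 0.061 = 4.0 practices, allowing for rounding.

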A recommendation for management will be included on the report according to the agreed management protocol after consideration of the patient's screening history and recorded presence or absence of symptoms.

Informing patients

Central recall (mail out)

If the test kit has been supplied directly from the central recall team, participants will be informed of their result by the central study nurse by a combination of letter, phone call, or text (preference will have been requested at the time of taking).

Practice taken or practice coordinated.

The patient will be informed of their result by the practice coordinating nurse or the patient's cervical screener by phone or text or letter as per normal practice.

Unsatisfactory

The test needs to be repeated at the patient's earliest convenience.

Negative hrHPV

A very low risk of cervical abnormality. Repeat screening test at normal recommended interval (*currently 3 years however will increase to 5 years with the new program*). However, if the patient has symptoms they should consult with their doctor. An exception to this is patients due to leave the NCSP screening programme. Please see Appendix 6.

Positive hrHPV (no reflex cytology)

The test has detected the presence of hrHPV. This indicates an increased likelihood of a cervical abnormality. Cervical cancer is very unlikely but further investigation is strongly recommended

HPV16/18

Participants positive for HPV 16 18 will be referred directly to colposcopy without delay. A cervical cytology test at this point is recommended but is not required.

HPV other

The patient will be advised to please make an appointment to undergo an examination and a cervical cytology test (smear) within 2 weeks by a cervical screener of their choice.

The making of appointments will be facilitated by the informant. The patient will be informed that there may be a charge for that appointment.

At this point a patient with a positive result may be referred to colposcopy if cytology triage is considered to be an unacceptable barrier, but the patient agrees to attend colposcopy.

Positive hrHPV with reflex cytology

If a cervical hrHPV sample has been taken and cytology triage has been performed, then this information and or the need to undergo colposcopy can be communicated with the patient face to face or by phone.

Referral to colposcopy

(See flow chart in Appendix 7)

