Referral to colposcopy guidelines are in accordance with planned NSU recommendations with the additional safety that patients with low grade cytology and hrHPV other who will be referred to colposcopy.

Referral to colposcopy is indicated for patients with a significant risk of high-grade cervical abnormalities. The recommendations in this pilot study have been agreed with the NCSP and take into consideration the current recommendations for colposcopy referral, risk of CIN2+, colposcopy service capacity, access to colposcopy for underserved populations, and the requirement of data collection from this study in a timely manner to inform implementation of the NCSP. It is important to acknowledge that these recommendations may differ to the final NCSP recommendations and time frames on the basis of this and other information yet to be determined.

Patients with hrHPV other and low-grade cytology are referred to colposcopy in this study because the burden of disease in this group is not documented in NZ. Within this study we are unable to follow up this group via repeated testing, in addition patients over 30 with low grade cytology and hrHPV are currently referred to colposcopy and laboratories are obliged to put this advice on their cytology reports. It is anticipated in the new program that these patients will undergo repeat testing at 12 and 24 months as per the Australian program.

Risk of CIN2+ can be stratified as below:

Low risk

- Other HPV positive, cytology normal or unknown

Intermediate risk

- HPV 16/18 positive with normal cytology
- Other HPV with ASCUS/low grade cytology (the risk for this group in NZ is unknown and may be low)

High risk

- HPV 16/18 positive with ASCUS/low grade/high-grade/AGC cytology
- Other HPV with high-grade/AGC cytology

Patients stratified as low risk will be recommended to have a repeat screen in 12 months.

Patients with intermediate risk will be referred to colposcopy as a semi urgent referral (for the purpose of the study we request these patients are seen within 3 months).

Patients with HPV 16/18 who do not undergo cytology may be referred as high risk because their risk is undetermined and may be high risk.

Patients with high risk of CIN2+ are referred for colposcopy (20 working days).

Patients with suspected cancer will be seen within 10 working days and treated accordingly as per regional practice.

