Clinical override will upgrade the urgency of referral including patients with an abnormal appearing cervix, symptoms, are under-screened or who have perceived barriers will be referred to colposcopy urgently at the discretion of the cervical screener.

Colposcopy and pathology records will be sourced via the provider (with permission of the patient).

Patients with positive hrHPV may be referred to colposcopy in the absence of cytology triage as follows: Pacific and Māori patients, under-screened patients, and patients with HPV16/18.

As identified by the Māori Steering Committee, cervical cytology testing is a probable barrier for Māori patients

(https://www.heiahurumowai.org.nz/_files/ugd/b7edfc_621f3417d3b84349be2ed6372d479d30.pdf). It is particularly important to fully discuss the indications for cervical cytology with patients and to explain that they are able to opt for direct referral to colposcopy without cytology screening, if they would prefer it.

Previous cervical abnormality may also be an indication for referral in the presence of an abnormal hrHPV test.

Colposcopy

Colposcopy will be performed as per standard practice guidelines. Patients who have had no cytology in the last 3 months or normal cytology should have a cytology performed. If feasible at least 1 biopsy should be taken of any visible lesion or the cervical transformation zone. Treatment protocols will adhere to NCSP guidelines. Relevant colposcopy and treatment data will be retrieved to be included in the study dataset.

Patients who do not attend for recommended cytology or colposcopy

The management of these patients should be consistent with normal practice.

Non-attendance for colposcopy is associated with a risk of cancer and every effort should be made to ensure attendance. Where possible a medical practitioner should discuss this with the patient and make an individualised plan for their follow up. The NCSP will be notified.

Patients with hrHPV other following a self-test who decline cytology may be referred to colposcopy. If this is declined where possible a medical practitioner should discuss this with the patient and make an individualised plan for their follow up. The NCSP will be notified. Support to Screen services will be utilised as per normal practice.

Data management

A detailed Data Management Plan is available as a separate document.

All patient data are confidential, and for Māori patients, data are recognised as taonga.

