In order to align with current NCSP practices, in terms of database requirements and automatic recall procedures, all patients in the clinician-taken sample group will have a cytology assessment of the sample they have already given, thus, do not need to return for a follow up cervical screen. The two groups, therefore, cannot be directly compared in terms of failure to return for follow up. In addition, as the clinician-taken and self-sample groups are self-selected they will be different and, hence, outcomes from the two groups will be recorded but cannot be directly compared.

Due to the relatively small size of this study and the unlikely outcome of a high-grade cervical abnormality, outcomes related to colposcopy referral will lack the power for stratification. However, the choice of screening method may usefully be able to be stratified.

Transfer of data and patient care to the NCSP.

The NCSPR will be informed of all patients participating in the study.

As the NCSPR is not currently able to manage the results of hrHPV screening this information will be overseen by the study team. The study team will act in place of the NCSPR to provide reminders to the practices when patients are overdue further investigations or repeat testing and to ensure management recommendations are correct. Following colposcopy or on completion of the study when the NCSPR is able to manage these patients' information they will be referred back to the NCSPR

Results of all cytology tests and hrHPV tests and colposcopy records will automatically be referred to the NCSPR. The study team will follow all patients to the end of the study to ensure patients who require colposcopy have been seen.

At completion of the study enrolled patients will fall under the following categories.

- Normal screen, next routine screen to be performed at the normal screening interval (5 years)
- Normal screen but because of previous abnormality follow up recommended in 12 months
- Abnormal screen referred to colposcopy attended follow up dictated by colposcopist and referred back to NCSP

- Abnormal screen colposcopy recommended lost to follow up/colposcopy declined
- Abnormal screen follow-up cytology advised but declined/lost to follow up
- Abnormal screen cytology performed follow up in 12 months recommended

This information will be shared with the NCSP (as far as possible in a manner that is suitable to the NCSP) and patients will be discharged to GP practice and NCSP

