Appendix 6 Flowchart for management of hrHPV results either clinician taken or vaginal self-test

*Note if a vaginal self-test is taken and the result is positive a cervical cytology specimen is indicated to stratify risk, however in some circumstances it will not change so is

not required. (i.e. HPV16/18 positive) If a cervical test has been taken this will be performed on the same specimen by the laboratory. It is advised that this test is performed within 2 weeks.

**With the new five yearly screening interval, those coming in for their next screening test (after previous cytology screening) any time in the last five years before age 69, i.e. 65 – 69 years of age (inclusive), can exit the programme if their hrHPV test result is negative. This includes those with normal screening histories, with no screening history and those with previous abnormalities who have already been returned to regular interval (three yearly) screening. Exceptions are:

1. Participants who are still in active surveillance following previous abnormalities need to complete their follow-up. So if a test of cure is indicated and hasn't been successfully completed then they need a test of cure – one negative HPV test is not sufficient in this circumstance.
2. Immune deficient participants with a negative hrHPV test need to return in three years for a repeat hrHPV screen, if this falls before 69 years of age
3. Women who have had a recent hysterectomy will need a test of cure if there is high-grade histology in the hysterectomy specimen, which may or may not have been preceded by high-grade cytology.

[figure not shown]
Those who would normally exit the NCSP under the current NCSP exit requirements i.e. have had two normal screening cytology samples between ages 62 and 69 years of age, can exit at 69 years of age without HPV testing (providing not immune deficient or requiring further follow-up because of abnormal results).

***Urgency of referrals to Colposcopy are as follows;

- **Very Urgent** – Suspicion of Malignancy (10 working days)
- **Urgent** – High-grade cytology and/or HPV 16 or 18 positive (20 working days)
- **Semi-Urgent** – other high-risk HPV and low-grade/ASCUS cytology (3 months)
- Colposcopy can be referred as a clinical override e.g. hrHPV other and patient declining cytology triage.

ASCUS: Atypical Squamous Cells of Undetermined Significance hrHPV: high risk human papillomavirus NCSP: National Cervical Screening Programme

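### Other hrHPV with unknown cytology is classed as low risk with a 12-month repeat, against the protocol's own triage steps and risk data

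*Protocol*

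**What the plan says.** In Referral to colposcopy, the low-risk stratum is "Other HPV positive, cytology normal or unknown". The action follows a few lines later: "Patients stratified as low risk will be recommended to have a repeat screen in 12 months". That sentence sets no separate condition for the patients whose cytology is unknown. The same section allows patients with HPV 16/18 and no cytology to be referred as high risk "because their risk is undetermined and may be high risk".

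Other parts of the protocol bear on the same patients:

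- **Informing patients, HPV other (no reflex cytology):** the patient is advised to "undergo an examination and a cervical cytology test (smear) within 2 weeks by a cervical screener of their choice".
- **Patients who do not attend for recommended cytology or colposcopy:** "Patients with hrHPV other following a self-test who decline cytology may be referred to colposcopy". If colposcopy is also declined, an individual plan is made and the NCSP is told.
- **Transfer of data and patient care to the NCSP:** one end-of-study category is "Abnormal screen cytology performed follow up in 12 months recommended". A separate one, with no interval, is "Abnormal screen follow-up cytology advised but declined/lost to follow up".
- **Appendix 6, first note:** after a positive self-test "a cervical cytology specimen is indicated to stratify risk". HPV 16/18 is the only example given where it is not required.

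**The concern.** When a positive self-test for other hrHPV is reported, cytology is unknown for every such patient. The section on informing patients gives that patient two weeks to have cytology; the low-risk line gives 12 months to a repeat screen. Cytology is what decides between a 12-month repeat and colposcopy in this group, so a missing result cannot be read as a normal one.

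Statistical Considerations names failure to return for cytology after a positive self-test as a key safety issue, and this line governs most of those patients. It also affects the safeguards. Appendix 2 has the study team check recorded recommendations against guideline. If the referral section is the reference, a 12-month recommendation without cytology passes that check. Yet Appendix 2 also counts failure to refer for cytology or colposcopy when due as a serious adverse event.

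**Working it through.** **1. Reproduce the protocol's figure.** Appendix 3, other hrHPV with normal cytology: 92/981 = 9.38% CIN2+, matching the stated 9.4%.

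**2. Risk by cytology, other hrHPV (Appendix 3 counts).**

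- Low-grade: (138 + 84)/(498 + 225) = 222/723 = 30.7%
- High-grade: 198/294 = 67.3%

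**3. Risk with cytology unknown.** This is the sum over cytology results of share × risk.

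| Mix (normal/low/high) | Low-grade risk | CIN2+ | Ratio to 9.38% |
|---|---|---|---|
| Appendix 3 pooled, 49.1/36.2/14.7 | 30.7% | (92+138+84+198)/(981+498+225+294) = 512/1998 = 25.6% | 2.7 |
| Appendix 4, 45/35, remaining 20% taken as high-grade | 30.7% | 0.45×9.38 + 0.35×30.7 + 0.20×67.3 = 28.4% | 3.0 |
| Appendix 4, 45/35/20 | as normal | 0.80×9.38 + 0.20×67.3 = 21.0% | 2.2 |
| Appendix 3 mix | as normal | 0.853×9.38 + 0.147×67.3 = 17.9% | 1.9 |
| High-grade 6.9% | as normal | 0.931×9.38 + 0.069×67.3 = 13.4% | 1.4 |
| Assumed 80/17/3 | as normal | 0.97×9.38 + 0.03×67.3 = 11.1% | 1.2 |

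The rows marked *as normal* use the Australian finding reported in Appendix 3, that low-grade risk is similar to normal. The 6.9% is (3,766 + 977 + 3,980)/126,429 from the large Appendix 3 table; it covers all hrHPV and is used only as a mix. The 80/17/3 mix is my assumption, to show a low end.

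**4. Which mix fits Appendix 4?** Per 1,000 screened: 1,000 × 7% × 75% = 52.5 with other hrHPV. The stated 8 urgent referrals give 8/52.5 = 15.2% high-grade, close to 14.7% and below the 20% remainder. Of the two rows with low-grade risk at 30.7%, 25.6% therefore fits better than 28.4%.

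**5. A directly stated figure.** Appendix 3 gives 6% CIN3 for HPV-positive patients with cytology unknown. Its large table gives 2.1% immediate CIN3+ for HPV-positive patients with normal cytology. Endpoint and population differ from step 3 (all hrHPV types), but the direction is the same.

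**6. Comparison with a stratum that is referred.** HPV 16/18 with normal cytology is classed as intermediate risk: (49 + 12)/(201 + 74) = 61/275 = 22.2% CIN2+.

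**7. Share who would have met the section's own colposcopy criteria had cytology been done.** Appendix 3: (723 + 294)/1998 = 51%. Appendix 4: 100 − 45 = 55%. Under the assumed 80% normal: 20%.

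**8. Patients to whom the line could apply.** Taking 75% of positives as other hrHPV (Appendix 4), self-test patients number 216 to 252 × 0.75 = 162 to 189 at 12% positivity (Statistical Considerations), or 1,800 to 2,100 × 7% × 0.75 = about 95 to 110 at Appendix 4's 7%. How many would remain without cytology cannot be derived.

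**The case against.** The strongest reply is that the low-risk line should be read in sequence. The reflex cytology section and the advice on informing patients both recommend cytology first, so *unknown* can mean patients still without it after that step. The referral section itself goes on to allow clinical override for under-screened patients and those facing barriers, and direct referral without cytology for several groups. Appendix 6 permits colposcopy when cytology is declined. Appendix 2 records non-attendance for cytology within 3 months as an adverse event and adds reminders. The recommendations were agreed with the NCSP, with colposcopy capacity in mind.

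Much of this stands. A reader might infer that the protocol skips triage, or that these patients have no route but a 12-month wait. The documents do not support that. The permissive referral wording and the override can also be read as exceptions to a 12-month default, so I do not count them as contradictions.

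The end-of-study list records status and is not a management rule, so it is weaker evidence. It does show where the authors expected the 12-month interval to apply. The HPV 16/18 comparison is also imperfect, because those patients are all referred and cytology sets only urgency. But in other hrHPV cytology decides referral itself, so missing cytology matters more there.

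None of these provisions makes unknown cytology low risk. Appendix 3's remark that triage will rest on the hrHPV result concerns patients who are referred, not those sent to a repeat. The Appendix 6 flowchart is not visible in the text reviewed, and nothing here relies on it.

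**Conclusion.** Wrong as written. The stated default for other hrHPV patients still without cytology is a low-risk 12-month repeat. This conflicts with the two-week cytology advice, the role Appendix 6 gives cytology, the end-of-study categories, and the section's own treatment of missing cytology in HPV 16/18.

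The document's data do not support equating unknown with normal: CIN2+ is 9.4% with normal cytology against roughly 11% to 28% with cytology unknown. The direction holds in every scenario, because the unknown group includes undetected high-grade cytology. The size is uncertain. It rests on overseas data, on the two Appendix 3 tables sharing a denominator, and on patients without cytology having the same mix as those with it.

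Two stronger readings are tempting. One is that the risk is about three times normal, or at least equal to the referred HPV 16/18 stratum. That holds only if low-grade risk is 30.7%; if it equals normal, the estimates (11% to 21%) all fall below 22.2%. The other is that about half of these patients would wrongly miss colposcopy. The share is 20% under the assumed 80% normal mix, and the number left without cytology is unknown.

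**What to change.** In Referral to colposcopy, delete the words *or unknown* from the low-risk line, so that it covers other hrHPV with normal cytology only. Then add that other hrHPV without cytology is of undetermined risk and is managed in this order:

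1. Cytology within 2 weeks, as already advised.
2. If cytology is not done or is declined, colposcopy may be offered, as already permitted.
3. If colposcopy is declined, an individual plan and notification of the NCSP.
4. The 12-month repeat only as the latest backstop for patients who decline both.

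The Appendix 2 check of recommendations should use this wording. The cost is a short amendment and possibly a few more colposcopy referrals. Referral stays permissive and the 12-month recall date is kept.
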